14 SAFETY EVALUATIONS

Safety analysis will be carried out for the initial 6-month period, the extension period, and the entire study period, respectively. For each of the periods, all subjects who receive at least one dose of study treatment in the corresponding period and have any post-treatment safety information will be included in the safety analysis. Safety will be assessed by examining the incidence, severity grade, and relationship to study drug of all treatment-emergent adverse events (TEAEs) reported during the study period. In addition, all other safety measures including clinical laboratory results, vital signs, electrocardiogram (ECG) and Echocardiogram (ECHO) values will be assessed. Unless otherwise specified, the baseline for safety endpoints is defined as the last non-missing assessment prior to the first dose. Numeric parameters will be summarized by descriptive statistics including n, mean, SD, median, minimum, and maximum. Adverse events will be summarized by number and percentage. Change from baseline will be calculated when both baseline and post-baseline results are non-missing numeric values.

For the initial 6-month period, unless otherwise specified, safety data will be presented for each cohort and all cohorts combined.

For the extension period, unless otherwise specified, safety data are summarized by dose level and all cohorts combined.

For the entire study period, unless otherwise specified, safety data are summarized by dose level and by cohort and all cohorts combined.

Subjects in Cohorts 1 and 2 may be represented at multiple dose levels and accounted once for each dose level they receive. Note the following rules are applied to associate the safety measure to a specific dose:

- AEs are associated to the dose taken on the start date of the AE.
- For mean summaries of safety parameters at visits over the course of the study the assessments on the day of escalation will be summarized under the previous dose.
- For mean summaries assessing pre and post dose measure on a specific day the assessments on the day of escalation will be summarized under the new dose.

For all summary tables for patients who discontinue treatment, all safety assessments within 30 days from the treatment discontinuation date will be included in summary tables.

14.1 Adverse Events

Adverse events will be coded in accordance with MedDRA version 19.1. A TEAE is defined as any AE that newly appeared or worsened in severity following initiation of study drug administration during the AE reporting period. After informed consent is obtained and the first administration of study drug, all non-serious AEs and SAEs reporting period begins and continues until 4 weeks following either the last administration of study drug or the early termination visit, whichever is longer. If the onset date or end date of an adverse event is partial, the same imputation rules described in Section 9 will be applied.

AEs are summarized by incidence rates and for specific tables also by exposure adjusted incidence rates:

- Incidence rates calculated as number of subjects with the event divided by the number of subjects in the population being assessed
- Exposure-adjusted incidence rates (EAIR) are calculated by dividing the total number of events by the total treatment exposure in the period under assessment for the subjects in the population being assessed. The exposure time for each subject is derived as the time from the date of first dose, to the date of the last dose in the period under assessment.

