Subjects will remain on a daily fixed dose throughout the initial 6-month treatment period. Subjects in each cohort continue to receive daily dosing (Cohort 1, 2.5 µg/kg; Cohort 2, up to 7.5 µg/kg, Cohort 3, up to 15 µg/kg, and Cohort 4, 30 µg/kg) for 6 months unless stopping criteria are met. When clinical safety is established and stopping criteria are not met after all 8-10 subjects have completed at minimum their first

10 days of cohort dosing, and after DMC review and approval, the subsequent cohort may be open to enrollment.

In the 18-month optional, open-label extension period, eligible Cohorts 1 and 2 subjects were dose escalated to the 15µg/kg dose while Cohort 3 and Cohort 4 subjects continued at their respective starting doses of 15µg/kg and 30µg/kg, respectively, based on the pre-specified dose adjustment criteria described in the protocol and amendments.

Figure 2.2.1: Study Design

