3.2 Data and Cohort Presentation

All available data for study BMN111-202 will be used for the final analysis. Efficacy data collected in study BMN111-901 that is 12 months prior to screening in BMN111-202 for subjects who subsequently enrolled in study BMN11-202, and are included in the corresponding analysis population, will be summarized in efficacy tables and figures.

For the initial 6-month period, unless otherwise specified, all data will be presented for each cohort and all cohorts combined.

In the extension period, efficacy and imaging assessment data will be summarized for Cohorts 1 and 2 subjects who switched to 15 μ g/kg by cohort, and Cohort 1 and 2 combined.

In the entire study period, efficacy and imaging assessment data will be summarized for Cohort 3 and Cohort 4 separately, and Cohort 3 and 4 combined.

In the extension period, all other data will be summarized by dose level and all cohorts combined. For the entire study period, unless otherwise specified, safety data are summarized by dose level, and by cohort, and all cohorts combined. Subjects in Cohorts 1 and 2 may be represented at multiple dose levels and are accounted once for each dose level they receive.

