14.1.1 All Adverse Events

The following summaries will be provided for each period:

- Overall Summary of AEs
- TEAEs by System Organ Class (SOC), Preferred Term (PT), and severity
- TEAEs assessed by investigators as related to study drug by SOC, PT and severity
- TEAEs by PT
- TEAEs by SOC
- Serious AEs (SAEs) by SOC and PT
- TEAEs leading to discontinuation by PT
- Incidence and exposure-adjusted event rates of TEAEs by SOC and PT

[figure not shown]
AEs of Special Interest

- Injection site reactions by SOC, PT, and severity
- Frequency and duration of ISRs
- ISR symptom by SOC, PT and severity
- Incidence and exposure-adjusted event rates of Hypotension TEAEs by SOC and PT
- Incidence and exposure-adjusted event rates of Heart Rate Change TEAEs by SOC and PT
- Incidence and exposure-adjusted event rates of events suggestive of Hypotension TEAEs by SOC and PT
- Incidence and exposure-adjusted event rates of Hypersensitivity TEAEs (SMQ) by SOC and PT
- Incidence and exposure-adjusted event rates of Hypersensitivity TEAEs (excluding ISRs) by SOC and PT
- Incidence and exposure-adjusted event rates of ISRs TEAEs by SOC and PT

Search criteria for the ADR/SMQ search criteria:

- Injection Site Reaction (ISR)
 - TEAEs are identified using having high level terms of MedDRA of ‘Injection Site Reaction’
 - ISR Symptom page, which captures additional symptoms associated with a specific ISR AE
- Hypotension
 - TEAEs are identified as PT: Blood pressure ambulatory decreased, Blood pressure decreased, Blood pressure diastolic decreased, Blood pressure orthostatic decreased, Blood pressure systolic decreased, Blood pressure systolic inspiratory decreased, Diastolic hypotension, Hypotension, Orthostatic hypotension
 - TEAEs suggestive of Hypotension are identified as PT: Fatigue, Nausea, Loss of consciousness, Vision blurred, Cold sweat, Dizziness, Syncope, Presyncope.
- Heart Rate Change
 - TEAEs of Heart Rate Change are identified as PT: Atrial tachycardia, Postural orthostatic tachycardia syndrome, Rebound tachycardia, Sinus tachycardia, Supraventricular tachycardia, Tachycardia, Tachycardia paroxysmal, Ventricular tachycardia, Bradycardia.
- Hypersensitivity – refer to BioMarin pharmacovigilance standard search terms
 - TEAEs – Broad Hypersensitivity SMQ (421 narrow and broad search term PTs)
 - [REDACTED]

A figure is provided for Mean Frequency of Injection Site Reactions by Month in Entire Study Period for all Cohorts by Dose

■ [REDACTED]

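### In the by-dose displays for the extension and the entire study, the severity, related, serious and discontinuation AE tables use crude percentages over unequal planned time at dose

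*SAP*

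**What the plan says.** **Measure.** SAP Section 14.1 says "AEs are summarized by incidence rates and for specific tables also by exposure adjusted incidence rates". It defines the default measure thus: "Incidence rates calculated as number of subjects with the event divided by the number of subjects in the population being assessed". Time does not enter that denominator.

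**Tables.** SAP Section 14.1.1 lists tables to be produced for every period. Four types carry no mention of exposure adjustment:
- "TEAEs by System Organ Class (SOC), Preferred Term (PT), and severity"
- "TEAEs assessed by investigators as related to study drug by SOC, PT and severity"
- "Serious AEs (SAEs) by SOC and PT"
- "TEAEs leading to discontinuation by PT"

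The table of all TEAEs by SOC and PT is titled as giving both incidence and exposure-adjusted event rates. So are the tables for hypotension, events suggestive of hypotension, heart-rate change, hypersensitivity and injection site reactions.

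**Layout.** Under SAP Section 14, safety data are shown by cohort in the initial 6 months, by dose level in the extension, and by both dose level and cohort over the entire study. An AE belongs to the dose taken on its start date. SAP Section 3.2 adds: "Subjects in Cohorts 1 and 2 may be represented at multiple dose levels and are accounted once for each dose level they receive".

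**Time at dose.** SAP Section 2.2 keeps every child on a fixed dose for the initial 6 months. In the extension, "eligible Cohorts 1 and 2 subjects were dose escalated" to 15 µg/kg, while Cohorts 3 and 4 stayed on 15 and 30 µg/kg. The protocol synopsis gives total treatment of up to 24 months. SAP Section 12 notes that switch times differ between children and advises caution with the switcher summaries. That remark concerns efficacy, and the visible text of Section 14 has no counterpart for AE percentages by dose.

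**The concern.** A crude percentage with an event rises with the length of observation. In a by-dose table, a child who switches contributes to the 2.5 or 7.5 µg/kg column only until the switch, whereas a Cohort 4 child contributes to the 30 µg/kg column for up to 24 months. If the true risk per unit time were the same at every dose, the columns observed for longer would still show higher percentages. A reader could take this for a dose-response in severe, related, serious or treatment-ending events.

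Safety and tolerability up to 24 months is the primary objective of the extension, so these displays matter. SAEs and discontinuations are likely to be infrequent, and the relative distortion is largest for infrequent events.

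**Working it through.** There is no planned figure to reproduce. SAP Section 2.4 reports no formal sample size calculation, and neither document states an expected AE rate.

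**Inputs**
- Shortest planned time on the starting dose: 6 months, 0.5 year (SAP Section 2.2).
- Upper end of low-dose time for switchers: about 1 year. This is inferred. SAP Section 12 plans a summary at the first visit with at least 12 months on 15 µg/kg, and 24 − 12 = 12 months. It is not a stated limit.
- Time on 30 µg/kg (Cohort 4), and on 15 µg/kg for Cohort 3: up to 2 years, taken as completed.
- First-event hazard λ: equal at all doses and constant, 0.1 to 0.5 per child-year. This is an assumption.

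**Crude percentage.** P(t) = 1 − exp(−λt).

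| λ per year | 0.5 y | 1 y | 2 y | Gap, 2 y − 1 y | Gap, 2 y − 0.5 y |
|---|---|---|---|---|---|
| 0.1 | 4.9% | 9.5% | 18.1% | 8.6 points | 13.2 points |
| 0.25 | 11.8% | 22.1% | 39.3% | 17.2 points | 27.6 points |
| 0.5 | 22.1% | 39.3% | 63.2% | 23.9 points | 41.1 points |

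The 2 y − 1 y column is a Month 12 switch and the 2 y − 0.5 y column a Day 184 switch. As ratios, 2 years against 1 year gives 1.90 at λ = 0.1 and 1.61 at λ = 0.5. Two years against 0.5 year gives 3.72 and 2.86.

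**15 against 30 µg/kg.** Take 16 switchers from Cohorts 1 and 2 plus 10 Cohort 3 children, with no dropout. Mean time on 15 µg/kg is (16 × 1.0 + 10 × 2)/26 = 1.38 years for a Month 12 switch and (16 × 1.5 + 10 × 2)/26 = 1.69 years for a Day 184 switch. At λ = 0.2 the pooled crude percentage is 23.8% or 28.6%, against 33.0% on 30 µg/kg.

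**Extension only.** At λ = 0.2 with 0.25 year left on the low dose, the crude percentages are 4.9% (low dose, 0.25 y), 22.1% (switchers on 15 µg/kg, 1.25 y) and 25.9% (Cohorts 3 and 4, 1.5 y).

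**With person-time.** Expected first events per child are 1 − exp(−λt). Expected time at risk up to the first event or end of time at that dose is [1 − exp(−λt)]/λ. The quotient is λ whatever t is, so every dose column has the same expected rate and the ratio is 1.0.

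**Precision.** With no events in T child-years, the exact upper 95% limit is −ln(0.025)/T = 3.69/T. Eight children for 0.5 year (T = 4) give 0.92 per child-year. Ten children for 2 years (T = 20) give 0.18.

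**The case against.** **An equal-window comparison is already planned.** All four table types are produced for the initial 6 months by cohort, when every child is on a fixed dose. A reader might infer that tolerability by dose cannot be read fairly anywhere in the plan. The documents do not support that, because the 6-month primary objective rests on unaffected tables. This objection stands and confines the point to the by-dose extension and entire-study displays. It does not remove the point, since the extension has its own safety objective. The entire-study by-cohort tables equalise planned total time but mix doses within Cohorts 1 and 2.

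**Four-fold differences are not the expected case.** A reader might take 0.5 against 2 years as typical. The extension rules in Protocol Section 9.1 argue against that for a whole cohort. A cohort's dose rises only after at least 6 months of data on all its subjects, and intermediate doses must have been tolerated for at least 6 months. Cohort 2 opened only after all of Cohort 1 had completed 10 days. A Day 184 switch from 2.5 to 15 µg/kg for all of Cohort 1 is therefore unlikely. This stands, and the Day 184 figures are an outer bound.

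**The exposure-adjusted tables.** These count events, so a reader might infer that they hide how many children are affected. They do not: their titles include incidence, which is a count of children. They do not, however, isolate serious, severe, related or treatment-ending events.

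**Other limits.** The hazards are assumed, and events clustered soon after first dosing would shrink the gap. The extension is optional, so not every Cohort 4 child need reach 24 months. Safety analysis is descriptive, and SAP Section 11 reports exposure duration by dose level, so an attentive reader can see the imbalance. Parts of Section 14.1.1 are blacked out, so a further output cannot be excluded. The point rests on the visible list.

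**Conclusion.** The concern holds for the four named table types in the by-dose extension and entire-study displays, and not beyond them. If the true risk is equal and constant, the doses with longer planned observation will show higher crude percentages.

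For 2.5 against 30 µg/kg the false gap is about 9 to 24 percentage points for a Month 12 switch, or roughly one to two children in a cohort of 10 (0.09 × 10 = 0.9; 0.24 × 10 = 2.4). The 13 to 41 points for a Day 184 switch are an extreme upper bound.

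These sizes assume an equal constant hazard of 0.1 to 0.5 per year, full 24-month follow-up at 30 µg/kg, and an inferred one-year upper end for low-dose time. The direction does not depend on the hazard chosen, but the size does.

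**What to change.** For the by-dose extension and entire-study versions of the four table types:

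1. Beside the crude percentage, add the number of children with a first event at that dose per child-year at risk at that dose, with an exact Poisson 95% CI.
2. Define exposure as time on the dose level concerned. SAP Section 14.1 now runs it from first to last dose within the period under assessment. Read literally, that could put a switcher's whole-study time into a low-dose denominator.
3. Footnote that crude entire-study percentages by dose are not for between-dose comparison, and refer readers to the initial 6-month tables by cohort for an equal window.

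A separate table limited to the first 183 days on each dose is not needed, since it would largely repeat the initial-period tables. If one is produced, show switchers to 15 µg/kg apart from Cohort 3, because switchers have already had at least 6 months of treatment.

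The cost is SAP and table-shell wording and a little more programming. SAP Sections 10 and 11 already summarise compliance and exposure by dose level, so no new data are needed. The intervals will be wide with 8 to 10 children per cohort.

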7.4 Summary of Overall Risks and Benefits

7.4.1 Summary of Risks from Nonclinical Studies

7.4.2 Summary of Risks from Clinical Studies

7.4.2.1 111-101

Based on review of the first-in-human Phase 1 study of BMN 111 in healthy adult volunteers, Study 111-101, BMN 111 administered SC daily was well tolerated with doses ranging from 0.5 µg/kg to 15 µg/kg. All AEs were of mild severity, and no SAEs were reported. The most common AE was mild, transient, self-limited orthostatic hypotension, of which the majority of cases were asymptomatic and observed only upon assumption of an upright posture following recumbence. No dose-limiting toxicities were identified outside of these CV findings.

7.4.2.2 111-202

Based on review of this ongoing phase 2 clinical trial, injection site reactions have been identified as risks associated with BMN 111 injections. Hypotension and hypersensitivity reactions are potential risks associated with BMN 111 injections. For a detailed summary of risks, please refer to the current IB.

	BMN 111-202 Amendment 4	Page 32
---	-------------------------	---------

In the phase 2 study BMN 111-202, injection site reactions were the most common AEs reported and are considered as an identified risk associated with BMN 111 injections. The most common injection site reactions across all cohorts included: injection site erythema, injection site swelling, and injection site urticaria. Of note, all injection site reactions have been reported as non-serious and grade 1 in severity, and no subjects have discontinued from the study or permanently discontinued study treatment as a result of the events.

The most important potential risks identified to date include hypotension (and complications related to hypotension and/or tachycardia) and the development of anti-BMN 111 antibodies. Anti-BMN 111 antibodies have the potential to mediate allergic reactions, reduce efficacy, and/or cross-react with endogenous CNP or other undefined agents. Anti-BMN 111 antibodies continue to be monitored in the study. No grade 2 or higher or serious hypersensitivity reactions have been reported to date. Reported adverse events of hypotension have been mild, non-serious, and have resolved without medical intervention. Both these potential risks will continue to be closely monitored.

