9.10.4.4 Vital Signs, Physical Examinations and Other Observations Related to Safety

9.10.4.4.1 Vital Signs

Vital signs will include seated systolic blood pressure (SBP) and diastolic blood pressure (DBP) measured in mm Hg, heart rate in beats per minute, respiration rate in breaths per minute, and temperature in degrees Celsius (°C). All treatment visits have pre-dose vital sign assessments. Post-dose assessments include heart rate and BP. On visit Days 1, 2, 3, and 4, minimum assessment frequency is every 15 min (± 5 min) for 2 hours post dose; and assessment is taken every 30 min (± 5 min) from 2 to 4 hours post dose. On visit Days 1 and 2, 4 to 8 hours post-dose measurements are taken every 60 min (± 10 min). For all other dosing visits, assessment is every 15 min (± 5 min) for the first hour post dose and a final assessment prior to the end of the visit (if longer than 1 hour). Vital sign assessment frequency is presented in [Table 9.10.4.4.1.1](#).

At Screening, after at least 5 minutes of rest, subject’s BP is taken in sitting position. Then the subject will stand and BP will be taken again at approximately 1 and 3 minutes after standing. At other visits, vital sign measurements are taken once per timepoint in a sitting position after at least 5 minutes of rest. Heart rate should be taken at each timepoint that BP is measured. When blood samples and BP assessments are scheduled at the same time or within the same time window, BP should be measured before blood samples are drawn. If a BP measurement must be taken after a blood draw, ensure adequate analgesia for the blood draw and wait several minutes before measuring BP. Vital signs may be monitored more frequently or for longer duration post-dose as clinically indicated ([Table 9.1.1](#)).

	BMN 111-202 Amendment 4	Page 71
---	-------------------------	---------

Table 9.10.4.4.1.1: Vital Sign Assessment Frequency

Vital Sign Assessment Frequency				
Screening	After at least 5 min of rest, subject's BP is taken in sitting position. Then the subject will stand and BP will be taken again at approximately 1 and 3 minutes after standing.			
	Assessment Frequency			
Dosing Visits	0-1 hr post-dose	0-2 hr post-dose	2-4 hr post dose	4-8 hr post-dose
Days 1, 2		q 15 min (± 5 min)	q 30 min (± 5 min)	q 60 min (± 10 min)
Days 3, 4 and dose adjustment visit in optional, open-label extension phase		q 15 min (± 5 min)	q 30 min (± 5 min)	

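### Calendar-time rates of hypotension and heart-rate TEAEs are not comparable across periods or dose columns, because post-dose BP and heart rate are scheduled on 12 of 183 days and then on 7 of about 547

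*SAP*

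**What the plan says.** SAP 14.1 defines the rate as follows: "Exposure-adjusted incidence rates (EAIR) are calculated by dividing the total number of events by the total treatment exposure in the period under assessment". Each subject's exposure time is "derived as the time from the date of first dose, to the date of the last dose in the period under assessment". SAP 14.1.1 lists, for each period, "Incidence and exposure-adjusted event rates of Hypotension TEAEs by SOC and PT" and "Incidence and exposure-adjusted event rates of Heart Rate Change TEAEs by SOC and PT". The Hypotension list consists of blood-pressure and hypotension terms, and the Heart Rate Change list of tachycardia and bradycardia terms. Symptoms such as dizziness and syncope are in a separate list of events suggestive of hypotension.

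Protocol 9.10.4.4.1 schedules post-dose BP and heart rate at dosing visits. Days 1 and 2 are followed for 8 hours and Days 3 and 4 for 4 hours. After that, "For all other dosing visits, assessment is every 15 min (± 5 min) for the first hour post dose", with one last reading if the visit runs longer. No BP or heart-rate measurement is specified for doses given away from the clinic.

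SAP 14 presents the initial phase by cohort and the extension by dose level. It adds: "For the entire study period, unless otherwise specified, safety data are summarized by dose level and by cohort and all cohorts combined". SAP 2.2 says that eligible Cohort 1 and 2 subjects moved to 15 µg/kg in the extension. No allowance for monitoring intensity is planned.

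**The concern.** A fall in BP or a change in heart rate without symptoms becomes an adverse event only if somebody measures it. Days without measurement add to the denominator but can add little to the numerator for such events. The share of such days differs between the initial phase and the extension. In the entire-study tables it also differs between dose columns, because the 2.5 and 7.5 µg/kg columns hold the densely monitored early months, while the 15 and 30 µg/kg columns also hold the sparsely monitored extension.

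Safety and tolerability are the primary objective of both phases, and Protocol 7.4.2.2 puts hypotension among the most important potential risks. A lower extension rate could be read as tolerance to the effect, and a flat dose trend as reassurance about the higher doses, when either may partly reflect visit frequency.

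**Working it through.** The plan states no event rate, so there is no figure to reproduce.

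**Inputs**
- Initial phase (Protocol Table 9.1.1): 12 dosing visits with vital signs, on Days 1, 2, 3, 4, 10, 15, 22, 29, 43, 85, 127 and 183, over 183 days.
- Extension (Protocol Table 9.1.2): 7 visits, at Months 8, 10, 12, 15, 18, 21 and 24, over 730 − 183 = 547 days.
- Escalated subjects: dose-adjustment and follow-up visits (Protocol 9.1 and Table 9.1.3). I assume 1 to 4 extra monitored days.
- *h*, the share of events on unmonitored days that are reported anyway. It is not given, so I show a range.

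**Monitored share of days, *d***
- Initial: 12/183 = 0.0656
- Extension: 7/547 = 0.0128
- Ratio: 5.12. With 1, 2 or 4 extra extension visits it is 4.5, 4.0 or 3.3.

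**Period comparison at constant risk per dose.** Recorded events per day are proportional to *h* + (1 − *h*)*d*.

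| *h* | Initial | Extension | Ratio |
|---|---|---|---|
| 0 | 0.0656 | 0.0128 | 5.12 |
| 10% | 0.1590 | 0.1115 | 1.43 |
| 25% | 0.2992 | 0.2596 | 1.15 |

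To read the table: at *h* = 10%, events on unmonitored days would make up 0.10 × (1 − 0.0656)/0.1590 = 59% of those recorded in the initial phase. At 25% they would make up 78%.

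**Entire-study dose columns.** Take a low-dose column of Days 1 to 183 (12/183) against a 24-month 30 µg/kg column (19/730 = 0.0260), with true risk per dose doubled. The observed ratio is 2[*h* + (1 − *h*)0.0260]/[*h* + (1 − *h*)0.0656].
- *h* = 0: 0.79, a reversal
- *h* = 1.3%: 1.00
- *h* = 5%: 1.33
- *h* = 10%: 1.55, an attenuation
- Switch at Day 364, *h* = 0: 2 × 0.0260/(15/364) = 1.26, counting the Month 12 visit in the low-dose column. It is 1.35 if that visit falls under the new dose (14/363). There is no reversal either way.

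For the 15 µg/kg column, assume 10 subjects in Cohort 3, and 16 subjects switching at Day 184 with two extra visits each. Monitored days are 10 × 19 + 16 × 9 = 334 over 10 × 730 + 16 × 547 = 16,052 days, or 0.0208. A true doubling then shows as 2 × 0.0208/0.0656 = 0.63 at *h* = 0, and reaches 1.00 at *h* = 2.3%.

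**By cohort, initial phase.** All four cohorts share one schedule, so *d* is the same and the ratio between cohorts is not distorted by scheduling.

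**The case against.** A reader might infer that the extension rate will be about five times too low and that the dose trend will be reversed. The documents do not support either as a general statement.

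- **Events can be reported from any day.** Protocol 9.4.1.1 requires at least 30 minutes of observation after every dose, by clinic, nurse or parent. Protocol 9.10.4.4.2 trains caregivers to recognise symptoms of hypotension. Telephone contact collects adverse events at least weekly, then every 2 to 4 weeks (Protocol 9.10.4.1). Five-fold is therefore a ceiling.
- **Reversal needs an early switch and almost no reporting.** Protocol 9.1 allows escalation only after at least 6 months of data for the whole cohort, with intermediate doses tolerated for at least 6 months. SAP 12 says that switch times differ between subjects. A switch near Day 183 is therefore the extreme case.
- **The adult evidence transfers poorly.** Protocol 7.4.2.1 describes orthostatic hypotension in the healthy-volunteer study, "of which the majority of cases were asymptomatic and observed only upon assumption of an upright posture following recumbence". In this trial, standing BP is scheduled only at Screening, and later readings are seated. That sentence does not fix the share of events here that only measurement would find.
- **Not every dose outside the scheduled visits is given at home.** Visits may be added on Days 5 to 9, and subjects may be dosed in the clinic until a parent is approved (Protocol 9.1 and 9.4.4).
- **Other summaries exist.** Subject incidence accompanies these rates, and SAP 14.3 summarises change from pre-dose to post-dose vital signs.

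The first four points limit the size of the effect but do not remove it. The SAP's separate symptom list makes it plausible that the BP-term list leans towards measured events. Calls also become less frequent in the extension, so symptom reporting may thin in the same direction. The last point does not answer the concern: subject incidence makes no allowance for monitoring, and vital-sign means are not event rates.

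**Conclusion.** The concern holds for events that depend on clinic measurement. Their calendar-time rate would fall by up to about 5-fold from the initial phase to the extension with unchanged risk per dose, or about 3.3- to 4.5-fold for escalated subjects. The fall is about 1.4-fold at 10% reporting on unmonitored days and 1.15-fold at 25%. Where the trial lies in this range cannot be told from the documents.

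In the entire-study dose-level tables, the bias attenuates a rising trend in favour of 15 and 30 µg/kg. It reverses a true doubling only with an early switch and reporting on unmonitored days below about 1% to 2%.

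These figures assume constant risk per dose over time, visits as scheduled, and the same reporting share in both periods. They count monitored days and ignore the longer observation on Days 1 to 4. The direction of the bias is clear and its size is uncertain, so this is an inexpensive improvement to a primary-objective safety comparison, not a flaw that invalidates it.

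**What to change.** Keep the planned exposure-adjusted rate. For the BP-based Hypotension list and the Heart Rate Change list, add to SAP 14.1:

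1. Events with onset on monitored dosing days, divided by the number of such days, by period and dose level. A monitored dosing day is a clinic dose with post-dose BP and heart rate, including dose-adjustment and unscheduled visits. With constant risk per monitored day, the ratio between periods becomes 1.0.
2. A separate count of events on unmonitored days. This shows how far recording depends on clinic measurement.
3. A footnote that calendar-time rates of these events are not comparable across periods or dose columns.

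Because Days 1 to 4 are observed for longer, any comparison limited to the first post-dose hour, which all dosing visits share, should use the timed vital-sign readings. It should not use adverse-event start dates, because the SAP assigns events to a dose by date and imputes partial dates.

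The cost is SAP wording and a few extra table columns, from visit dates and vital-sign data already collected. The downside is that extension rates will look less favourable.
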